7.10 Other Institutions and Physicians	29
8. RECORDS AND REPORTS	30
8.1 Investigator Records.....	30
8.2 Investigator Reports	30
8.3 Sponsor Records.....	31
8.4 Sponsor Reports.....	32
APPENDIX A: DEFINITION OF TERMS	33
APPENDIX B: TIMELINE	37

Table of Figures

Figure 1: Corox OTW Bipolar LV Leads	11
---	-----------

Table of Tables

Table 1: Implant Success Rate Comparison	7
Table 2: Corox BP LV Lead: Pacing Parameters	8
Table 3: Comparison of Freedom from Adverse Events in the Corox BP LV Lead to Other Published Study Results	9
Table 4: Adverse Event Exclusions	13
Table 5: Primary Safety Endpoints Sample Sizes	16

CELESTIAL POST-APPROVAL REGISTRY

PROTOCOL SIGNATURE PAGE

The signature below constitutes the receipt and review of the CELESTIAL protocol and any attachments, and provides the necessary assurances that this registry will be conducted according to all stipulations of the protocol, including all statements regarding confidentiality, and according to local legal and regulatory requirements and applicable U.S. federal regulations, ICH and GCP guidelines.

PRINCIPAL INVESTIGATOR:

Signed: _____ Date: _____
Name (please print)

Signature Date: _____

PROTOCOL SUMMARY

Title:	CELESTIAL Post-Approval Registry
Design:	This study is a long-term post approval registry designed to follow at least 2500 patients implanted with BIOTRONIK's Corox BP left ventricular lead. Each patient will be followed for 5 years.
Purpose:	The purpose of this post-approval registry is to confirm long-term safety and successful biventricular pacing for BIOTRONIK's Corox BP left ventricular (LV) pacing leads as used in conjunction with any BIOTRONIK CRT pulse generator (CRT pacemaker (CRT-P) or CRT defibrillator (CRT-D)). The evaluation of safety will be based on the analysis of Corox BP LV lead related adverse events. The CELESTIAL post-approval registry will provide data to permit characterization of any LV lead failures contributing to patients losing CRT. Additionally, acute and chronic LV lead parameters for pacing thresholds and impedance will be evaluated.
Patient Population:	Patients who require treatment for advanced heart failure through any CRT-P or CRT-D. Patient must be successfully implanted with a BIOTRONIK CRT system, including a Corox BP LV lead, from 7-180 days prior to enrollment.

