2. STUDY DESIGN

The CELESTIAL post-approval registry is a multi-center, prospective, non-randomized, 5 year data collection registry. The registry is designed to gather long term safety and reliability data on BIOTRONIK's Corox BP LV leads. All patients enrolled into the clinical study will have an implanted BIOTRONIK CRT system, including a Corox BP LV lead, and will be enrolled from 7-180 days after successful CRT implantation or system revision.

Patients will be followed for 5 years post-implant, and are meant to be seen according to each institution's standard of care, but not to exceed a follow up time frame of (1) every 6 months for CRT pacemakers (CRT-Ps) or (2) every 4 months for CRT defibrillators (CRT-Ds). At enrollment, information will be collected regarding patient medical history, demographics, and other secondary data or data of interest specifically pertaining to the implant and status of the LV lead. At each follow up, a determination will be made whether the system is providing appropriate biventricular pacing. Additionally, the electrical parameters of the left ventricular lead will be collected, and any LV lead related adverse event will be documented.

The primary safety endpoints are constructed to capture all LV lead-related serious adverse events (SAEs) that require additional invasive intervention to resolve. Individual analysis of each serious adverse event (SAE) will be conducted and reported throughout the study. The low probability of SAE mandates the registry study size of a minimum of 2000 patients.

A secondary effectiveness endpoint will utilize a responder analysis of the success/failure of the CRT generator implanted with the Corox BP LV lead to deliver long-term biventricular pacing through 5 years post-implant.

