2.7 DATA ANALYSIS

For both primary safety endpoints 1 and 2, pooling of data from the Corox OTW BP, Corox OTW-S BP, and Corox OTW-L BP LV leads will be justified as part of the final data analysis. The differences in outcomes for the Corox OTW BP, Corox OTW-S BP, and Corox OTW-L BP LV leads will be tested using an exact, Chi-square test. If no evidence is found of differences between the Corox OTW BP, Corox OTW-S BP, and Corox OTW-L BP LV leads ($p > 0.05$), then the results will be considered poolable for purposes of testing the protocol hypotheses associated with the two primary endpoints. If evidence of differences is found for a given endpoint, then the hypotheses for that endpoint will additionally be tested separately for each LV lead.

CELESTIAL REGISTRY PROTOCOL

Primary safety endpoint 1 will be evaluated by performing an exact, noninferiority test comparing a binomial proportion (overall SAE free-rate at 5 years) to 92.5%, with a noninferiority delta of 5%. Equivalently, the upper, one-sided 95% confidence bound for the absolute difference between the overall SAE free-rate and 92.5% must not exceed 5%.

The evaluation of primary safety endpoint 2 will be based on the exact, two-sided 95% confidence interval for the observed, individual SAE rates at 5 years. The upper bound of these 95% confidence intervals must be less than 1%.

The secondary endpoint of successful biventricular pacing will be summarized as a success rate at each of the scheduled CELESTIAL follow-up visits through 5 years post-enrollment, together with the associated exact, 95% confidence intervals.

The secondary endpoint of other SAEs at 5 years, which were excluded from the primary safety analyses (listed in Table 5), will also be summarized as SAE rates together with their associated exact, 95% confidence intervals.

The secondary endpoints of pacing threshold and impedance measurements for the Corox BP LV leads will be summarized at scheduled visits where they were evaluated, using standard measures, including means, standard deviations, medians, minimums, and maximums.

The secondary endpoint for overall incidence of serious adverse events that meet the primary endpoint 1 criteria will be evaluated separately for each Corox BP lead model using the criteria established for primary safety endpoint 1 and 2.

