3.2.5 Routine and Unscheduled Follow-Ups

Patients enrolled in the CELESTIAL post approval registry can be implanted with either a CRT Pacemaker (CRT-P) or a CRT Defibrillator (CRT-D). Follow-up schedules for these devices vary by practice, but typically occur every 3-4 months for a CRT-D and every 6 months for a CRT-P. Therefore patients will be seen for routine follow-up visits per their institutional standard of care, but not to exceed every 6 months. All scheduled follow up windows are ± 1 month.

Any time a patient is seen outside of a required follow-up window according to each site's pre-determined specific follow-up scheduling practice, that visit is considered an unscheduled follow-up. Each site Principal Investigator (PI) and Clinical Research Coordinator (CRC) will be trained to identify and schedule follow-ups to meet this expectation. Additionally, the EDC will provide assistance in identifying properly scheduled follow-ups according to this protocol by assisting in the selection of the proper electronic Case Report Form (eCRF).

The following are required at each follow-up visit:

- Interrogate programmed parameters
- Determine lead electrical parameters
- Evaluate device diagnostics and programmed parameters to ensure CRT is programmed "ON" and the device is correctly providing CRT therapy
- Record % of CRT pacing
- Determine if there are any cardiac-related Adverse Events. If there are, complete the Adverse Event eCRF
- Complete all appropriate eCRF's

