1. At implant, pacing thresholds for the permanently programmed electrode that are greater than 3.0 Volts at 0.5 ms., or
2. At follow-up, pacing thresholds for the permanently programmed electrode that are greater than 3.5 Volts at 0.5 ms.

ERI – Elective Replacement Indicator

Exit Block – The failure of an intact pacing system to capture the heart because the stimulation threshold exceeds the output of the pacemaker

Explanted (LV Lead) – Surgical removal of an LV lead during the acute implant stage, whereby the lead has not been chronically implanted and can be easily removed by simple traction

Extracted (LV Lead) - Surgical removal of a chronically implanted LV lead

Failure to Capture or Loss of Capture – Intermittent or complete failure to achieve cardiac stimulation at programmed output delivered outside of the cardiac refractory period

High Pacing Threshold – Sudden and significant increase compared to the previous measured threshold value

IDE – Investigational Device Exemption

Insulation Breach/Break – Visual, electrical, or radiographic evidence of a disruption or break in the insulation of a lead

IRB – Investigational Review Board

Lead Dislodgment or Lead Migration – Radiographic, electrical or electrocardiographic evidence of electrode displacement from the original implant site or electrode displacement that adversely affects pacing, and/or lead performance

Lead Fracture – Visual, electrical and/or radiographic evidence of mechanical break within the lead conductor (connectors, coils and/or electrodes)

Lead impedance out of range – Pacing impedance is considered abnormal if a measurement is ≤ 200 Ohms or ≥ 2000 Ohms

Loss of Sensing/Undersensing– Intermittent or complete failure to sense any intrinsic events that occur outside the programmed refractory periods at programmed sensitivity settings

LV – Left Ventricular

LV Lead Abandoned, CRT programmed off – The LV lead remains connected to the generator but LV pacing is disabled

Non-healing Pocket Dehiscence – Separation of wound edges around the pocket of the implanted pulse generator that have not healed

CELESTIAL REGISTRY PROTOCOL

NYHA – New York Heart Association, a recognized system of classifying patient condition according to:

- I – Ordinary physical activity does not cause undue fatigue, palpitation, dyspnea, or anginal pain
- II – Ordinary physical activity results in fatigue, palpitation, dyspnea, or anginal pain

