### 5.3 SECONDARY ENDPOINTS

There are no formal hypothesis tests associated with the secondary endpoints.

#### 5.3.1 Secondary Endpoint 1

Secondary endpoint 1 examines the successful biventricular pacing in a BIOTRONIK CRT device at scheduled CELESTIAL registry follow-up visits. The mean, standard deviation, minimum, and maximum of the biventricular pacing percentage will be reported for each visit. This endpoint will be evaluated using the subject population defined in section 3.1 Intention-to-Treat (ITT) Analysis Population.

#### 5.3.2 Secondary Endpoint 2

Secondary endpoint 2 examines the rates of serious adverse events excluded from primary safety endpoint. The serious adverse event rates will be reported along with a Kaplan-Meier actuarial graph and case summary will be reported to assess this endpoint. The estimated freedom from adverse event at 5 years along with the standard error and 95% confidence intervals will also be reported. This endpoint will be evaluated using the subject population defined in section 3.1 Intention-to-Treat (ITT) Analysis Population.

#### 5.3.3 Secondary Endpoint 3

Secondary endpoint 3 examines the sensing, pacing threshold, and pacing impedance measurements for the Corox LV leads at scheduled CELESTIAL registry follow-up visits. The mean, standard deviation, median, minimum, and maximum of each measured values be reported for each visit. This endpoint will be evaluated using the subject population defined in section 3.1 Intention-to-Treat (ITT) Analysis Population.

#### 5.3.4 Secondary Endpoint 4

Secondary endpoint 4 examines the individual electrical parameters of the Corox OTW BP LV lead, the Corox OTW-S BP LV lead, and the Corox OTW-L BP LV lead. The electrical parameters presented will be the sensing, pacing threshold, and pacing impedance measurements for each lead model at scheduled CELESTIAL registry follow-up visits. The mean and standard deviation of each measured value will be

reported for each visit. This endpoint will be evaluated using the subject population defined in section 3.1 Intention-to-Treat (ITT) Analysis Population.

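### Secondary endpoint 1 summarizes only the biventricular pacing percentage, so nothing in it would mark a visit with a non-capturing LV lead as unsuccessful

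*SAP*

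**What the plan says.** The Protocol Summary gives confirmation of successful biventricular pacing as part of the registry's purpose, and says the registry will "provide data to permit characterization of any LV lead failures contributing to patients losing CRT". Secondary endpoint 1 serves that purpose.

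The protocol treats it as a success/failure endpoint. Section 2 (Study Design) states: "A secondary effectiveness endpoint will utilize a responder analysis of the success/failure of the CRT generator". The same section says that at each follow-up "a determination will be made whether the system is providing appropriate biventricular pacing". Section 2.7 (Data Analysis) adds: "The secondary endpoint of successful biventricular pacing will be summarized as a success rate at each of the scheduled CELESTIAL follow-up visits", with exact 95% confidence intervals. Neither document defines success or appropriate pacing.

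Protocol 3.2.5 lists two separate tasks for each visit. One is to evaluate diagnostics and programming to ensure that CRT is on and "the device is correctly providing CRT therapy". The other is "Record % of CRT pacing". Programmed parameters and lead electrical parameters are also required.

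SAP 5.3.1 keeps only the second task: "The mean, standard deviation, minimum, and maximum of the biventricular pacing percentage will be reported for each visit". It has no success criterion, no success rate and no capture condition.

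Appendix A defines loss of capture as: "Intermittent or complete failure to achieve cardiac stimulation at programmed output delivered outside of the cardiac refractory period".

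**The concern.** By the protocol's own definition, output can be delivered without the heart being stimulated. A pacing percentage and effective resynchronization are then different quantities, and the difference arises when the LV lead fails to capture. That is one of the failures this registry is meant to characterize. An endpoint named for successful biventricular pacing but analysed through the percentage alone has no step at which such a visit would count against it.

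At stake is the interpretation of the registry's effectiveness result. A high mean percentage at five years would be read as durable CRT delivery, although the analysis does not use the capture information gathered at the same visits. Restoring the protocol's success rate would not cure this by itself: a rate derived only from the percentage would have the same gap.

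**Working it through.** **No figure to reproduce.** The documents give no sample size, power, margin or success threshold for secondary endpoint 1, and SAP 5.3 states that no formal hypothesis test applies to the secondary endpoints. The check is therefore a tracing exercise plus an illustration.

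**Step 1: follow one visit through the plan.** Suppose CRT is on, the recorded percentage is high, and the LV threshold exceeds the programmed output.

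- Secondary endpoint 1 (SAP 5.3.1): the high percentage enters the mean. Nothing marks the visit.
- Secondary endpoint 3 (SAP 5.3.3): the threshold enters a separate summary and is not compared with that patient's output.
- Secondary endpoint 2 (SAP 5.3.2): the event counts only if it is a reportable adverse event. Under the note in Protocol 7.6, a problem corrected by reprogramming other than polarity or pacing mode, with no invasive action, is not reported.
- Primary endpoint 1: high threshold and intermittent or absent LV capture are excluded (Protocol Table 4).
- FDA-requested analysis (SAP 2.4 and 5.4): elevated thresholds at routine visits from day 30 count even without a reportable event. Appendix A sets elevated at follow-up as above 3.5 V at 0.5 ms, so a lower threshold that still exceeds a low programmed output would not qualify on that basis. The result is an event rate, not a statement about CRT delivery at a visit.

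Capture is thus examined in several places, but none feeds into endpoint 1.

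**Step 2: illustrate the size.** Overstatement of the mean = m × f × u, where:

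- m = percentage recorded in affected patients, assumed 97 (not in the documents).
- f = 3.6% to 5.6%, the Table 4 range for high threshold, intermittent capture or no capture.
- u = share of those cases unresolved at the visit, assumed 0.1, 0.5 or 1.0.
- Effective LV pacing in unresolved cases is taken as 0, and the percentage is assumed to count delivered pacing.

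| u | f = 3.6% | f = 5.6% |
|---|---|---|
| 1.0 | 97 × 0.036 = 3.49 points | 97 × 0.056 = 5.43 points |
| 0.5 | 1.75 | 2.72 |
| 0.1 | 0.35 | 0.54 |

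The choice of m matters little. At u = 1, m = 90 gives 3.24 to 5.04 points and m = 98 gives 3.53 to 5.49.

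**Step 3: compare with sampling error.**

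- For the mean, with an assumed SD of 10 points and n = 1000: SE = 10/√1000 = 0.316, and the 95% half-width is 1.96 × 0.316 = 0.62 points. The overstatement passes this when u exceeds 0.62/5.43 = 0.11 (f = 5.6%) or 0.62/3.49 = 0.18 (f = 3.6%).
- For a success rate derived from the percentage alone, the misclassified share would be f × u: 0.36 to 0.56 points at u = 0.1, 1.8 to 2.8 at 0.5, and 3.6 to 5.6 at 1.0. The exact 95% interval for an assumed 95% rate is 93.5-96.3% at n = 1000 (half-width 1.4) and 94.1-95.8% at n = 2500 (half-width about 0.9).

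On these assumptions the effect exceeds sampling error at u = 0.5 and 1.0, and stays within it at u = 0.1.

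**The case against.** The strongest reply has four parts.

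**The counter is not described.** A reader might infer that the percentage is known to ignore capture. The documents do not say how it is counted, and Protocol 3.1.1 allows any current or future CRT device from the sponsor. This stands: the overstatement is conditional. The missing success criterion and capture condition are not.

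**The endpoint may concern delivery by the generator.** Protocol 2 speaks of the generator, and 2.1 of delivery by the CRT devices. A delivery percentage fits that wording. But the Protocol Summary ties successful pacing to the LV lead, and 3.2.5 does not treat the percentage as the whole of the CRT check. This part stands only in part.

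**Capture is covered elsewhere.** A reader might infer that the registry is blind to capture loss. It is not: lead parameters are taken at every visit, and secondary endpoints 2 and 3 and the FDA-requested analysis report capture or threshold problems. What remains is the missing link to endpoint 1. Nor are patients who have lost capture scored as successes, since SAP 5.3.1 scores nobody.

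**The size is soft.** Table 4 gives event rates from prior studies, not the prevalence of lost capture at a visit. The category includes high thresholds at which the lead may still capture. Reportable events also need an action under Condition Two of Protocol 7.6, often surgery or disabled pacing, so many would be resolved by the next visit. This stands, and makes the upper figures unlikely.

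**Conclusion.** The point holds as a gap in how secondary endpoint 1 is analysed. The SAP reduces a success/failure endpoint to a summary of one percentage, and nothing in it would class a visit with a non-capturing LV lead as unsuccessful. That follows from the documents alone.

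The numerical consequence depends on the percentage counting delivered pacing and on how many capture problems are unresolved at a visit. The documents settle neither. About 0.35 to 5.4 points is an illustration, not an estimate, and a reader should not take Table 4's 3.6-5.6% as the share of visits affected.

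The endpoint is secondary and untested, and no primary conclusion changes. The correction is still worth making, because without it the endpoint cannot answer the question its name poses.

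**What to change.** In SAP 5.3.1, add the per-visit success rate with exact 95% confidence interval that Protocol 2.7 specifies. For analysis, count a visit as successful only if all of these hold:

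- CRT is programmed on.
- The visit determination required by Protocol 2 and 3.2.5 is that biventricular pacing is appropriate.
- The LV threshold measured at that visit does not exceed the LV output as found at interrogation, compared at the same pulse width.

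Count absent or intermittent LV capture, or LV pacing off, as not successful. The output as found is needed because reprogramming during the visit would otherwise hide the failure. Pulse width matters because Appendix A states thresholds at 0.5 ms but quotes a maximum device output at 1.5 ms.

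Keep the raw percentage as a separate descriptive summary, tabulated by same-visit capture status. Do not set it to 0% on the strength of one test, since the documents do not say what period the percentage covers. State how it is counted, and report the number of visits that cannot be classified.

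Cost: SAP wording and one derived variable, with no change to patient management. Protocol 3.2.5 already requires programmed and lead electrical parameters at each visit, though the case report forms are not shown and the field-level detail should be confirmed. Some visits will be unclassifiable where pulse widths differ, and the reported figure may be slightly less favourable.

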2.1 STUDY ENDPOINTS

This clinical investigation includes the assessments of two primary safety endpoints related to the Corox BP LV leads, and several secondary endpoints that include an evaluation of the long-term delivery of biventricular pacing by BIOTRONIK CRT study devices. The hypotheses associated with the primary safety endpoints are presented below.

2.2 PRIMARY ENDPOINT 1: SAFETY OF COROX BP LV LEADS PACING – OVERALL COMPLICATION-FREE RATE

The purpose of primary endpoint 1 is to evaluate the overall incidence of serious adverse events that require additional invasive intervention to resolve, related to the Corox BP LV leads implanted with either BIOTRONIK CRT-P or CRT-D devices.

Primary safety endpoint 1 is constructed to capture all LV lead-related serious adverse events, not limited to fractures and insulation failures, but excluding those well documented adverse events that do not reflect a LV lead failure.

The following serious adverse events have been collected and reported by each LV lead manufacturer in their respective Summary of Safety and Effectiveness Data Reports (P050045, P050023, P030035, P010031, P010015, and P010012). While these SAEs will not be counted toward primary endpoint, they will be collected and analyzed as pre-specified secondary endpoints.

Table 4: Adverse Event Exclusions

Adverse Event Exclusions	Estimates of rates from prior studies
Inability to place LV Lead	10 - 14%
Lead dislodgements up to 180 days post implant procedure	1.9 - 9%
High LV pacing threshold, intermittent LV capture, no capture of LV lead	3.6 - 5.6%
Diaphragmatic/pectoral stimulation	0.2 - 2.9%
Infection	1.6 - 2.3%
Atrial lead, ICD lead, or generator adverse events requiring additional interventions	1.6 - 36.8%
Non LV lead related hospitalizations	27.4 - 48.9%
Non LV lead related death	6.2 - 18.9%
Implant procedure related complications such as CS dissection, CS perforation, pneumothorax, arrhythmias, cardiac tamponade, hematoma	1.5 - 13.3%
LV lead related thrombosis	<0.5%
Implant damage to LV lead (e.g. accidental cut to lead body during pocket revision, device replacement, etc.)	0.2 - 0.9%
Twiddler's syndrome	0.2%

Assuming that the expected Corox BP LV lead-related serious adverse event rate (proportion of subjects with at least one SAE), excluding the above, is 7.5% or less, then the primary safety endpoint will be evaluated in the following testable hypothesis in a noninferiority format.

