For the sample size calculation, a maximum loss to follow-up of 10% per year (50% over 5 years) was assumed. The loss to follow-up rate encompasses all causes for subjects to be exited from the study, including subject death, device explants, patient directed withdrawals, physician directed withdrawals, and loss of contact with the subject. BIOTRONIK will make every effort to limit the loss to follow-up, for reasons other than subject death and device explants unrelated to device design or performance, to less than 20% of the total registry enrollment cohort.

Minimum cohort size

The pre-specified secondary analysis will be conducted as an ad hoc analysis, meaning no testable hypothesis is being stated. Therefore, the minimal cohort size to analyze each lead model is based on an assumption of an equal 1/3 distribution of each lead model being enrolled in the CELESTIAL Registry. For the evaluation of the Corox OTW-L BP lead, a minimum of 600 evaluable subjects will be necessary.

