2.7.2 Missing Data

The reasons for any missing data in the study will be documented. The sponsor will examine both missing-data patterns, which describe which values are observed and which are missing, and the missing-data mechanisms, which concern the relationship between missingness and the values of variables in the study data set [R.J.A. Little and D.B. Rubin, 2002, Statistical Analysis with Missing Data, 2nd edition, Wiley and Sons].

For evaluation of the primary study endpoints (safety endpoints 1 and 2), only patients who achieve 5 years of follow-up or have experienced a serious adverse event prior to 5 years will be included in the evaluation of the associated hypotheses. The secondary endpoint of other SAEs at 5 years, excluded from the primary safety analyses, will be analyzed in similar manner. There will be no imputation for these missing adverse event outcomes.

For purposes of Kaplan-Meier actuarial analyses, described in Section 2.7.1 Trend Analyses, all SAE data on enrolled patients will be included, with follow-up time censored at the time of withdrawal or last completed follow-up visit.

Secondary endpoints, which include successful biventricular pacing, pacing thresholds, sensing and impedance measurements will be analyzed in two ways. Initially, all available results will be summarized by scheduled visit through the 5 years of study follow-up. Afterwards, a last value carried forward (LVCF) will be used to estimate the values at the final 5-year follow-up evaluation.

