#### 3.1 INTENTION-TO-TREAT (ITT) ANALYSIS POPULATION

The intention-to-treat (ITT) population includes all subjects enrolled in the study. The ITT subjects have documentation of informed consented and implant of the Corox LV study lead. This population includes all subjects enrolled in the study.

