## **5.4 FDA REQUESTED AD HOC ANALYSIS**

The FDA requested ad hoc analysis examines the overall incidence of events defined in section 2.4. The FDA defined event rates will be reported along with a Kaplan-Meier actuarial graph and case summary will be reported to assess this analysis. The estimated freedom from adverse event at 5 years along with the standard error and 95% confidence intervals will also be reported. This endpoint will be evaluated using the subject population defined in section 3.1 Intention-to-Treat (ITT) Analysis Population.

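### SAP 5.3.2 names no row-level 5-year estimator and no rule for death for the Table 4 event rates, so late-accruing rows can be misstated, and Protocol 2.7.2 prescribes a conflicting analysis set

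*SAP*

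**What the plan says.** Protocol 2.4 and SAP 2.3 define secondary endpoint 2 as the rates, through 5 years, of the events listed in Table 4. The table has twelve separate rows, one of which is "Non LV lead related death".

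SAP 5.3.2 gives the analysis: "The serious adverse event rates will be reported along with a Kaplan-Meier actuarial graph", plus a case summary. It adds: "The estimated freedom from adverse event at 5 years along with the standard error and 95% confidence intervals will also be reported". The set is ITT, and SAP 3.1 states: "The intention-to-treat (ITT) population includes all subjects enrolled in the study". No denominator or interval is given for the rates. Nothing says that the curve is run by event type, whereas SAP 5.3.5 asks for its curve by lead model. Death is not mentioned.

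Protocol 2.7 says that this endpoint "will also be summarized as SAE rates together with their associated exact, 95% confidence intervals". Protocol 2.7.2 analyzes it in the manner of the primary endpoints, that is, on subjects who reach 5 years or have an event. For the trend curves of Protocol 2.7.1, the data are used "with follow-up time censored at the time of withdrawal or last completed follow-up visit". Attrition is planned at a maximum of 10% per year, 50% over 5 years (Protocol 2.6; SAP 5.6), and Protocol 2.6 explains: "The loss to follow-up rate encompasses all causes for subjects to be exited from the study, including subject death".

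SAP 5.4 uses the same format for the FDA-requested analysis: "The FDA defined event rates will be reported along with a Kaplan-Meier actuarial graph".

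**The concern.** The Table 4 events are those taken out of both primary endpoints, so their 5-year rates show what the primary result leaves out. A reader will want them row by row, and three features of the plan stand in the way.

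- A plain count over all enrolled treats a subject who withdrew in year 1 as event-free for 5 years. Exits by death do not cause this error, because a dead subject can have no later event. Other exits do.
- One pooled Kaplan-Meier curve over all of Table 4 estimates freedom from any such event. It says nothing about infection or generator events alone.
- If the curve is run by row with death censored, 1-KM estimates risk as though nobody died, which exceeds the proportion of patients who have the event.

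Separately, the two documents prescribe different sets for the same endpoint. The Protocol's set drops event-free subjects who leave early but keeps early leavers who had an event, so it pushes rates upward.

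**Working it through.** **The plan's own figures.** SAP 5.3.2 states none. The attrition input reproduces the enrollment figures in Protocol 2.6 and SAP 1.1: 1000/0.5 = 2000 and 240/0.5 = 480. Compounding 10% per year would give 1 - 0.9^5 = 41%, so 50% is the simple sum. Both totals were run.

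**Inputs from the documents**
- Total exit by 5 years: 50%, a planning maximum that includes death.
- Protocol 2.6 aims to hold exits other than death and unrelated device explants below 20% of enrollment. At 50% total that leaves (50 - 20)/50 = 60% of exits as death or such explants. All of these are treated as deaths here.
- Illustrative true 5-year proportion: 5.6%, the top of Table 4's prior-study range for the high-threshold and capture row.

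**Assumptions not in the documents.** Hazards are constant and independent. The clock starts with follow-up, ignoring the 7-180 days between implant and enrollment. The death share of exits, s, is varied from 0 to 100%.

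**Formulas.** Total exit hazard h = ln 2/5 = 0.1386 per year; death hazard d = s × h; event hazard λ.
- True proportion (death competing) = λ/(λ+d) × [1 - exp(-5(λ+d))]
- Plain n/N = λ/(λ+h) × [1 - exp(-5(λ+h))]
- 1-KM, death censored = 1 - exp(-5λ)
- Completers-or-event rate = (n/N) / [(n/N) + exp(-5(λ+h))], counting the row's own event

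**Worked case, s = 60%.** d = 0.0832, and a true 5.6% requires λ = 0.01415.
- True: 0.1453 × 0.3853 = 5.60%
- n/N: 0.0926 × 0.5341 = 4.95%
- 1-KM: 1 - exp(-0.0707) = 6.83%
- Completers-or-event: 0.0495/(0.0495 + 0.4659) = 9.6% (9.0% at s = 40%)

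A simulation of this case gave 4.95% for n/N and 5.61% for the true proportion.

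**Range for a true 5.6% with 50% exit**

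| Death share of exits | n/N | Relative error | 1-KM | Relative error |
|---|---|---|---|---|
| 0% | 4.05% | -28% | 5.60% | 0% |
| 40% | 4.64% | -17% | 6.40% | +14% |
| 60% | 4.95% | -12% | 6.83% | +22% |
| 80% | 5.27% | -6% | 7.27% | +30% |
| 100% | 5.60% | 0% | 7.73% | +38% |

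With 41% exit the ranges are 0-22% low and 0-28% high; at s = 60% they are 9% low and 16% high. For a true 48.9% (the top of the hospitalization range) with 50% exit and s = 60%, n/N is 43.95% (10% low) and 1-KM is 58.04% (19% high).

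**Where the problem is small**
- Events confined to the first 180 days, as in the dislodgement row: n/N is 0-3.4% low and 1-KM 0-3.5% high.
- Pooled composite: non-LV-lead death is an event, so Kaplan-Meier is adequate. Suppose the nonfatal events alone would reach 40% at 5 years, and s = 40% with all deaths counted as non-LV-lead. Then the true value is 1 - 0.60 × exp(-5 × 0.0555) = 54.5%, and Kaplan-Meier gives the same. Plain n/N gives 45.8%.

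**The case against.** The strongest reply is that SAP 5.3.2 never labels the plain rate a 5-year rate. The 5-year label belongs to the Kaplan-Meier estimate, which has a standard error and interval and handles early exit, and SAP 3 chose ITT so as not to be limited to completers. SAP 5.3 also states that no formal test attaches to the secondary endpoints. All of that stands and limits the point to descriptive reporting. It does not supply a row-level 5-year figure, which an endpoint worded as rates through 5 years needs.

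Several stronger readings are tempting, and the documents do not support them.
- A reader might infer that the plan censors death for this endpoint. The censoring sentence in Protocol 2.7.2 is written for the trend curves of 2.7.1 and does not name death. SAP 5.3.2 is silent.
- A reader might infer that every row will be printed as two figures bracketing the truth. That requires a curve per row, and the more natural reading of SAP 5.3.2 is one pooled curve.
- A reader might take the definition in Protocol 2.2, a proportion of subjects with at least one event, as governing these rows. It defines the lead-related rate after Table 4 events are excluded. The exact intervals in Protocol 2.7 do point to a proportion of patients, but that is an inference.
- A reader might conclude that no reported figure is usable for any row. Early rows are nearly right either way, and Kaplan-Meier suits the death row and the composite. Failure to place the lead does not arise as an initial-implant outcome, because Protocol 3.1.3 admits only successfully implanted patients.

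**Conclusion.** The point holds for rows that accrue late: hospitalization, generator and other-lead events, infection, and high threshold or loss of capture. For these, SAP 5.3.2 as written yields a plain rate that reads low and no row-level 5-year estimate. A row-by-row Kaplan-Meier would read high if death were censored.

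The central figures, about 12% low and 22% high in relative terms, rest on constant independent hazards, the maximum 50% exit, and 60% of exits being deaths. The two errors trade off: n/N is right if every exit is a death, and 1-KM is right if none is. In absolute terms the 5.6% row moves by about 0.65 points down (5.60 - 4.95) or 1.23 points up (6.83 - 5.60).

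The conflict with Protocol 2.7.2 is firmer because it is textual, and its effect is larger: 5.6% becomes about 9.0-9.6% under the 40% and 60% death shares. No test decision changes. This should be settled before the final analysis, as a matter of correct description.

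**What to change.** In SAP 5.3.2, for each Table 4 row that can occur after enrollment, report on the ITT set the 5-year cumulative incidence with a 95% confidence interval, using the Aalen-Johansen estimator with death as a competing event and other exits censored. Use Kaplan-Meier for the death row. Label any pooled Kaplan-Meier curve as a composite. Show n/N as an observed count, with its denominator, and not as a 5-year rate.

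Align Protocol 2.7 and 2.7.2 with this, so that both documents give one population and one type of interval. In SAP 5.4 the cumulative incidence could optionally be added beside the FDA-requested Kaplan-Meier estimate, which stays.

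The cost is SAP and Protocol wording, standard software and one more table. No new data collection is needed: Protocol 4.1 already lists a Study Exit form, and Protocol 7.8 asks for the date of death where available.
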